2.5.1 Disaster Responder Community Advisory Group

After disaster strikes, a Community Advisory Group will be created to provide continued advice on the study and outreach efforts. The group will consist of up to 15 members representing local communities, organizations representing worker groups, as well as various occupational groups and is expected to engage in the following activities:

- Facilitate dialogue between disaster responder community members and the study team
- Identify effective communication strategies and vehicles tailored to the disaster responder communities' needs
- Assist in the dissemination of study related information locally and regionally
- Host disaster responder community meetings
- Proactively identify issues of concern with study implementation and options for resolutions
- Retain participants in the registry over time

A Community Advisory Group chair will be carefully selected from among its members and will work in close collaboration with the study investigators. The Community Advisory Group will meet regularly throughout the entire study duration.

2.6 Example Implementation of this Protocol

To help illustrate how this protocol will be executed, an example is described in Appendix D: Examples of Protocol Implementation During a Disaster Scenario of the actions the study team would take to implement the protocol under the described disaster scenario. While a hurricane scenario is used to describe a possible use of this protocol, the RAPIDD protocol is intended to be adaptable for use in any disaster of research interest.

3 Study Objectives

3.1 Primary Objective

The primary objective is to create a research registry comprised of disaster response workers who are rostered before or immediately after deployment to a disaster area.

3.2 Secondary Objectives

Secondary objectives are:

- To gather sociodemographic, health status, occupational exposure, and lifestyle information of the cohort before or immediately after deployment to a disaster area
- To collect, process and store biological samples to allow estimations of disaster-related exposures of the disaster response worker cohort before or immediately after deployment to a disaster area
- To establish a well-characterized disaster response worker cohort that will allow for future analyses of associations between disaster exposures and health outcomes

4 Study Design

4.1 Description of the Study Design

This is a registry study conducted to establish and characterize a cohort of disaster responders deployed to a disaster area to conduct emergency response activities. The registry data and samples will be available for use in future scientific investigations, which will require additional scientific and ethical reviews.

4.1.1 Recruitment

In most cases, it is anticipated that recruitment will primarily occur in a group setting adjacent to the disaster site (e.g., disaster worker staging area). There may also be situations when groups of potential participants are pre-identified (e.g., from a roster of disaster responders obtained prior to their deployment); in this case attempts to contact possible cohorts of interest to promote study enrollment may be made.

If feasible, the study may be advertised and potential participants may be contacted through various mechanisms (e.g., email, phone, flyer, text message, approached at a disaster site or training session) as part of an overall study recruitment strategy. Recruitment strategies will be sensitive to the fact that

disaster responders are engaged in critical emergency operations that may be prioritized over research considerations.

All of the methods used to recruit participants would provide an overview of the study and ascertain participant interest. The RAPIDD team will develop study brochures and FAQs (Frequently Asked Questions) that can quickly inform prospective participants of study aims. Interested individuals who are a part of a cohort of interest may be asked to provide contact information as part of the recruitment process so that they may be contacted and provided with further information for attending a registry visit at the work site (see Section 4.1.2).

Study documents and recruitment materials are currently developed in English, but speakers of other languages may be included depending on the disaster responder community involved. Translated materials will be developed for these populations and submitted as an amendment to the IRB for approval. Effective strategies for the development of culturally appropriate recruitment materials for the study cohort will be determined by soliciting participation and input from representatives of the target cohort. Bilingual study staff will work with non-English speaking individuals to the extent possible for anticipated languages (e.g., Spanish). The study team may also use telephone or video remote interpreter services (e.g., LanguageLine) in order to effectively communicate with non-English speakers. Remote interpreter services maintain their own code of confidentiality, but in addition to this, all interpreters will sign confidentiality agreements specific to RAPIDD.

Due to the variability inherent in disaster responses, the coordinating center, Social & Scientific Systems, Inc. (SSS), will determine and implement the most appropriate recruitment strategy based on the context of the situation. Only recruitment materials that have first received IRB approval will be used in the field.

4.1.2 Registry Visit

The registry visit may be scheduled, or the visit may occur unscheduled (e.g., during just-in-time training at the staging area) prior to deployment to the disaster area. The visit will consist of an explanation of the study and its expectations by a study staff member who is qualified and approved to obtain informed consent. The candidate will be allowed to ask questions and the study staff will allow ample time for the candidate to make an informed decision. Individuals who are eligible to participate and provide written consent will be enrolled, assigned a unique study ID number, and will undergo study procedures to collect baseline biological specimens, health information, or questionnaire responses according to **Table 1** in [Section 6](#). Any additional study procedures will be described in Appendix B: Protocol Amendment Checklist during a protocol amendment process.

4.1.3 Visit Reminder Contacts

Most registry visits will occur immediately. In rare cases where a future visit has been scheduled with a participant, the study staff may use phone calls, email, or text reminders to inform a participant of the date and time of his/her upcoming visit at the work site or to confirm he/she will be able to attend.

4.1.4 Reports to Participants and Referrals

During each registry visit, study staff will collect measurements including: height and weight to calculate BMI, blood pressure, pulse oximetry and spirometry. The participant will receive handouts with the results of these tests/measurements, standardized clinical interpretations, and advice for seeking care (see Appendix E: Medical Referral Values and Recommended Actions). In addition to providing the participant with results, handouts and recommended actions, participants who do not have a primary care provider or who cannot afford to pay for care may be referred to a local clinic that provides care for services based on a sliding scale. The referral handout consists of a list of health resources and mental health resources including the DHHS Health Resources and Services Administration (HRSA) "Find a Health Center" search page and the Substance Abuse and Mental Health Services Administration (SAMHSA) treatment facility locator search page.

In the rare event where the clinical exam visit yields immediately actionable medical data (e.g., dangerously low/high blood pressure or O₂ saturation), trained study staff will immediately inform the coordinating center site manager and facilitate, if necessary, the administration of emergency care. The study staff will be responsible for ensuring appropriate follow-up care until the event resolves or stabilizes and the participant is under the care of a licensed medical provider.

It may be many years before participant samples are tested. Participants will not receive individual results from the future analysis of samples unless the analysis yields an abnormal value.

4.1.5 Registry Duration and Contact Updates

Once this cohort is registered, it is possible that the scientific community will be interested in conducting follow-up with this cohort for 10 years or longer depending on its size, what is learned from future analyses and scientific and/or public health need. Throughout the duration of the registry, we may occasionally email or send a letter to participants asking them to complete and return a form updating or confirming their contact information. Any mailings that are "returned to sender" will undergo tracing efforts to identify updated contact information. The participant will be informed when enrolling in this study that participation in future studies is voluntary.

4.2 Study Endpoints

A goal of the RAPIDD Study is to establish a well-characterized disaster response worker cohort that will allow for future analyses of associations between disaster exposures and health outcomes. While certain health outcomes in the disaster response worker cohort may be anticipated based on past disaster experience, the study is designed to allow for the investigation of a wide range of outcomes of interest for a given disaster scenario. These health outcomes may include, but are not limited to, the following areas: respiratory, cardiovascular, hematologic, dermatologic, neurologic, mental health, oncologic, reproductive, immunologic, hepatic and renal impacts.

5 Study Population

The population to be studied are disaster responders deployed to a disaster area to conduct emergency response activities. Disaster responders may include traditional first responders such as police, fire, and emergency medical personnel, as well as non-traditional responder groups such as public health personnel and workers involved in environmental remediation and restoration activities.

The following inclusion and exclusion criteria will be used to establish eligibility, and will be reviewed with participants prior to enrollment to verify eligibility. There are no enrollment restrictions with regard to gender, race, or ethnic background.

5.1 Participant Inclusion Criteria

At the time of screening, study candidates must meet **all** of the following inclusion criteria to be enrolled:

- INCL 1.* At least 21 years of age
- INCL 2.* Is part of an eligible disaster responder cohort as defined in [Section 5](#) that has received IRB approval for inclusion

5.2 Participant Exclusion Criteria

Study candidates who meet the following exclusion criterion cannot be enrolled:

- EXCL 1.* Any conditions that, in the opinion of the Investigator, would pose an unacceptable risk to the participant or to the validity of the study results

6 Study Procedures

Table 1 List of Study Procedures

Procedure	Estimated Time (min)			Protocol Section
	Enhanced Set	Basic Set	Core Set	
Informed Consent	10	10	10	9.3
Vital Signs	2	2	N/A	6.1
Pulse Oximetry	2	2	N/A	6.2
Anthropometry	2	2	N/A	6.3
Spirometry*	15	N/A	N/A	6.4
Biospecimen Collection	30	15	5	6.5
Questionnaire Administration	20	10	5	6.11
Total Estimated Time	81	41	20	

*Only performed for participants who are eligible per the study inclusion/exclusion criteria (see Sections 5.1 and 5.2) after informed consent has been obtained (see Section 9.3).

All study procedures that may be included in the execution of this protocol during a specific disaster research response are outlined in **Table 1** and further described in Sections 6.1 – 6.11. In order to optimize flexibility, this protocol is scalable to a range of disaster situations. Three proposed sets of procedures (**enhanced, basic and core**), which vary by participant time burden, technical requirements, and available infrastructure, are described in the sub-sections below. In the early phases of disaster response when responder groups may have significant limitations in their available time for study, the core set of procedures option may be implemented which includes the self-collected biospecimen collection option (see Section 6.5.3) and the administration of a brief core registry questionnaire. We estimate that the core option would require 20 minutes of participant time. Conversely, the enhanced set of procedures option may be implemented in situations when responder groups have sufficient time available to allow a more comprehensive collection of health data and biospecimens (see Section 6.5.1). We estimate that the enhanced option would require approximately 80 minutes of participant time if consent for all study procedures are received and completed.

It is important to note that the composition of these procedure sets are only recommendations and may be revised at the time of the disaster to assure that the most appropriate set of study procedures for the situation are conducted. Our rationale for this standardized approach to procedural composition is that it allows us to develop in advance comprehensive specimen collection and processing documents, training manuals, along with materiel and equipment load lists so that these are readily available for the immediate research response to an evolving disaster. The specific set of procedures completed during a given disaster scenario may be a subset of these planned procedures. For example, workers may be without electrical power in the field, removing the option to collect samples that must be refrigerated or processed (e.g., centrifuged) on site. Study staff will refer to the Field Operations Guide (FOG) developed for each disaster for a description of the procedures from this protocol to be completed (and the order in which they will be completed) in the field.

While the planned procedures listed in **Table 1** represent a spectrum of data and specimens that would provide broad utility to future studies, it may be that novel procedures (e.g., dermal scrapings, neurobehavioral testing) are requested to investigate the unique circumstances of an individual disaster. In these situations, the RAPIDD study team will recommend an appropriate set of procedures and modify the RAPIDD protocol via the IRB amendment process. Study staff who administer the study procedures will have the necessary education, qualifications, and experience to conduct these activities. Study-specific training will be provided by the coordinating center (SSS) and research staff will be certified in each procedure administered in the protocol.

No specific diagnoses or pathology investigations are planned for the biological specimens or health information collected under this protocol. However, future research conducted under other research protocols may include such investigations.

All samples and data will be labeled and tracked using the participant's study ID. All participants will be asked to provide their contact information, age, gender, race, and ethnicity. The demographic questions are included in the core registry, basic health registry and enhanced health registry questionnaires (see [Section 6.11](#)). Age is the only demographic variable that determines eligibility. Data on gender, race, and ethnicity [required for National Institutes of Health (NIH) human participants reporting] are only used to characterize the study population.

No findings will be reported to the participant's employer (in fact, registry forms do not collect employer data) and it will be made clear to all participants, through the consent, that the RAPIDD Study does not supersede any occupational examination to determine fitness for deployment (i.e., participants cannot be included/excluded from deployment to a disaster response based on individual RAPIDD results) and that no testing for illegal drugs will be performed on participant samples.

6.1 Vital Signs

Vital signs recorded will include resting heart rate and blood pressure, which will be measured using standard clinical oscillometric equipment. In the core set of procedures option in **Table 1**, vital signs may be skipped to save participant time.

6.2 Pulse Oximetry

Oxygenation of the participant's hemoglobin will be measured using a pulse oximeter, with the sensor placed on a thin part of the body, such as a fingertip or earlobe. In the core set of procedures option, pulse oximetry may be eliminated to reduce participant time burden.

6.3 Anthropometry

Study staff will record measurements of weight (kg), height (cm), and hip and waist circumference (cm). Height will be measured with a portable stadiometer

or self-reported. Weight will be measured with a digital scale or self-reported. Hip and waist circumference will be measured with a reusable vinyl (or equivalent flexible) measuring tape.

6.3.1 Body Mass Index

Height and weight will be used to determine body mass index (BMI), which will be calculated according to one of the following equations:

$$\text{BMI} = \frac{\text{weight in kilograms}}{(\text{height in meters})^2} \quad \text{OR} \quad \frac{[\text{weight in pounds}] \times 703}{[(\text{height in inches})^2]}$$

6.4 Spirometry

Spirometry will be conducted according to American Thoracic Society (ATS) guidelines ([6](#), [7](#)).

Spirometry will be performed using a portable, transit time-based spirometer (e.g., EasyOne, ndd Medical Technologies, Inc., Andover, MA, USA, or a comparable model). All spirometers will undergo standard quality control checks each day they are used. A full Forced Vital Capacity (FVC) maneuver will be conducted to obtain three ATS-acceptable forced expiratory maneuvers, with a maximum of eight attempts allowed.

Spirometry will be conducted with the participant seated and wearing a disposable nose clip. New, individually-packaged, disposable mouthpieces and new spacers will be used for each participant.

To the extent possible, participants will be asked to not use their asthma inhalers on the day of the examination, and the timing and dosage of all asthma medications taken over the preceding seven days will be recorded.

Study staff conducting spirometry will be trained by coordinating center research staff familiar with collecting spirometric data in the field. Following training, staff will be required to submit 5 practice tests that are judged as acceptable by the pulmonary function testing software and will receive certification from coordinating center research staff. If computer-generated quality scores are lower than expected, coordinating center research staff will provide feedback along with suggested corrective actions to the study staff performing spirometry.

Exclusion from Undergoing Spirometry

Participants with a blood pressure >180 mmHg systolic or >110 mmHg diastolic, or with a heart rate >100 or <40 beats per minute will not undergo spirometry during the visit. Additionally, participants who answer yes to any of the following questions will also not be tested:

- In the past three months, have you had any surgery to your chest or abdomen?
- In the past three months, have you had a heart attack or stroke?

- In the past three months, have you had a detached retina or have you had eye surgery?
- In the past three months, have you been hospitalized for any other heart problem?
- Are you currently taking medication for tuberculosis?

These exclusion questions include those used in BOLD (8) and PLATINO (9), two multi-national studies that enrolled over 14,000 adults >40 years old for pre- and post-bronchodilator spirometry, administered by trained technicians. No adverse events occurred in either the BOLD or PLATINO studies. These exclusions are considered very conservative and these questions are not generally asked prior to spirometry maneuvers.

It is estimated that spirometric testing will require 15 minutes to conduct. In situations when available participant time is limited (basic and core sets), it may be skipped.

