9.4.3 Risks Associated with Spirometry

Spirometry is a very low-risk procedure with few side effects. Participants may experience transient coughing, lightheadedness, dizziness, fainting (more commonly in older persons with impaired lung function), and chest tightness. These symptoms usually resolve after the test is complete.

To minimize risks associated with this procedure, very conservative exclusions for undergoing spirometry will be implemented, testing is done in a seated position, and study personnel will be trained to look for signs of dizziness or other problems and will stop the maneuver if necessary.

Any risk of transmitting infection from one participant to the next through the use of shared equipment is minimized by using disposable nose clips, spacers, and

mouthpieces (spirettes), which have the additional protection of a built-in bacterial filter.

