10.3.3 Adverse Event Surveillance Period

Surveillance for AEs will include the time period from when informed consent is obtained at the registry visit until completion of the visit. At the end of each visit, participants will be asked if they experienced any problems during the visit. Participants will also be instructed to contact the study staff if they experience any new problem within two days of a visit.

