10.3.4 Reporting of Adverse Events

Only clinically significant adverse events (based on the investigator's medical judgment) will be reported to the IRB. Examples of clinically significant adverse events include:

- Fainting during spirometry or blood collection
- Respiratory distress induced by spirometry that requires medical attention
- Prolonged bleeding, hematoma formation, or infection associated with blood collection that requires medical attention

Field staff will be trained to detect and respond to clinically significant adverse events, and will be expected to report clinically significant adverse events to the coordinating center immediately.

At the time of the continuing IRB review, the PI will provide an aggregate summary of all clinically significant AEs.

Given the minimal risk of the procedures contained in the protocol, we anticipate SAE's to be very infrequent and therefore should be reported regardless of cause or association with preexisting conditions. The PI will report SAEs to the NIEHS IRB and NIEHS Clinical Director as soon as possible, but not more than 7 days after the PI first learns of the event.

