10.3.6 Management of Adverse Events

Any participant reporting an AE/SAE will be evaluated and managed appropriately by study staff. This could include immediate management at the study site, facilitation of emergency care, or referral to a primary care physician, public health clinic, or specialist.

The study staff will be responsible for ensuring appropriate follow-up care until the event resolves or stabilizes, and no more follow-up is required.

11 Data/Records Management

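### Section 6.4 asks participants to forgo asthma inhalers for the whole examination day, without ending the request at the spirometry test or exempting rescue inhalers

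*Protocol*

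**What the plan says.** Section 6.4 of the protocol describes how spirometry is done and who is excluded from it. On asthma medication it says: "To the extent possible, participants will be asked to not use their asthma inhalers on the day of the examination". The same sentence adds that "the timing and dosage of all asthma medications taken over the preceding seven days will be recorded". No other statement about inhalers was found in Section 6.4, in the spirometry risk section (9.4.3) or in the adverse event sections (10.3 to 10.3.6).

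On the risks of the test, Section 9.4.3 states: "Participants may experience transient coughing, lightheadedness, dizziness, fainting (more commonly in older persons with impaired lung function), and chest tightness". It adds that these effects usually pass once the test is over, and that "study personnel will be trained to look for signs of dizziness or other problems and will stop the maneuver if necessary". Section 10.3.4 lists, among its examples of clinically significant adverse events, "Respiratory distress induced by spirometry that requires medical attention".

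On what happens around and after the test, Section 10.3.3 says: "Surveillance for AEs will include the time period from when informed consent is obtained at the registry visit until completion of the visit". It continues: "Participants will also be instructed to contact the study staff if they experience any new problem within two days of a visit". Section 10.3.6 says: "Any participant reporting an AE/SAE will be evaluated and managed appropriately by study staff".

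On timing, Section 4.1.2 allows an unscheduled registry visit at the staging area before deployment, and Section 4.1.3 says that most visits happen at once rather than by appointment.

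**The concern.** A request to withhold inhalers before spirometry has an obvious purpose: to obtain a measurement unaffected by a recent dose. That purpose is served once the last maneuver is done. The period named in Section 6.4 is nevertheless the day of the examination, and the sentence makes no distinction between a maintenance inhaler and one kept for relief of symptoms.

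What is at stake is the safety of participants with asthma. The protocol itself says that the test can provoke chest tightness and, as an example of a reportable event, respiratory distress. Someone who follows the sentence to the letter would be holding back the medication meant for such symptoms, possibly on a day when they go on to disaster work.

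The wording also matters because of how this protocol is used. Section 2.3 places procedure descriptions in the main body because they are expected to stay the same from one disaster to the next, and Appendix D envisages that the review board will look only at the new material at activation. A loose sentence in Section 6.4 may therefore carry into each use of the protocol.

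**Working it through.** No arithmetic applies. The check is whether any part of the protocol ends the request at the test, exempts rescue inhalers, or keeps inhaler users out of spirometry.

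1. **Period of the request.** Section 6.4 gives the day of the examination. It does not say before the test, or until the test is complete. No other section reviewed supplies an end point.

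2. **Which inhalers.** Section 6.4 refers to participants' asthma inhalers without distinction. The only relief is the general qualifier at the start of the sentence, which limits how firmly the request is made. It does not tell a symptomatic participant that use is allowed.

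3. **Whether inhaler users are tested.** The specific exclusions in Section 6.4 are blood pressure above 180 systolic or 110 diastolic, heart rate above 100 or below 40, and five questions: recent chest or abdominal surgery, recent heart attack or stroke, recent retinal detachment or eye surgery, recent hospitalisation for another heart problem, and current tuberculosis medication. None concerns asthma or recent inhaler use. The general criterion in Section 5.2 leaves room for the investigator's judgement, but does not name asthma. Inhaler users are therefore expected among those tested, as the medication record in Section 6.4 also implies. Up to eight attempts are allowed.

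4. **Recognised effects of the test.** Section 9.4.3 includes chest tightness, and Section 10.3.4 includes respiratory distress. Neither section lists withholding an inhaler as a risk or says what a participant should do with one.

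5. **Safeguards.** Staff watch for problems and stop the maneuver (9.4.3), respond to clinically significant events (10.3.4), and manage any reported event (10.3.6). Formal surveillance ends with the visit, after which the participant is told to report new problems arising within two days (10.3.3). These steps reduce the risk, but none of them changes or lifts the inhaler request.

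6. **When the request is heard.** Since most visits are immediate (4.1.3), many participants may first hear it at the visit. For them it can do little about doses taken earlier that day. Read literally, what it governs is the remainder of the day, which may include deployment (4.1.2).

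7. **Whether the measurement needs the wider period.** It does not. Inhaler use after the last maneuver cannot alter the spirogram. For use before it, the record of timing and dosage over the preceding seven days already shows which tests followed a dose.

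Steps 1, 2 and 5 show that the gap in the wording is not closed elsewhere in the protocol. Step 7 shows that closing it costs the measurement little.

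**The case against.** The strongest reply is that context supplies the limit. The sentence sits among the preparations for the test, it is only a request, it is qualified, and it is joined to a medication record that looks backwards from the examination. A sensible reader would take it to mean abstention beforehand. In addition, Section 9.4.3 says that symptoms usually resolve when the test is over. Section 6.4 reports no adverse events in two multinational spirometry studies with over 14,000 adults, whose exclusion questions are among those used here. Participants will hear the request from trained staff working from a Field Operations Guide and a consent form that are not shown and may be clearer.

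Most of this stands. The likely intent is conceded, the request is soft, and serious trouble after the test is not what the protocol expects. It also cannot be said that participants will be given the sentence in this form. What remains is that the protocol is the governing text for the procedure, and it states a period longer than its purpose requires without saying that symptom relief is permitted.

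Three stronger readings are tempting and are not supported:

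- **A stated number of hours at risk.** A reader might count from the end of the visit to midnight. The documents give no visit start times, and the count would describe a literal reading that is probably not the intended one. It would not measure risk.
- **A flaw in the Appendix E referral table.** A reader might infer that results after a recent dose will lead to the wrong advice, because the spirometry rows do not mention medication. Any size for that effect would rest on assumed changes in FEV1. A participant with an index still below its lower limit is referred on either side of the 50% boundary, dose timing is already recorded, and the results handouts, which might carry a label, are not shown.
- **Bias in the cohort's lung function data.** Nothing in the documents shows how many participants use inhalers or take a dose before testing, and the medication record allows later analyses to deal with it.

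**Conclusion.** The point holds as a minor wording defect with a participant-safety aspect. Section 6.4 asks, softly, for abstention from all asthma inhalers on the examination day; it neither stops at the test nor exempts rescue use. The protocol recognises that the test can cause chest tightness and respiratory distress, and the visit may come just before deployment.

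The conclusion rests on the text alone and on one assumption: that staff or participants could take the sentence as it is written. No numerical size can be given. The number of participants concerned and the length of any exposure cannot be derived from the documents, and neither is claimed. The objectives, sample size, power and planned analyses are unaffected.

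**What to change.** Reword the sentence in Section 6.4 along these lines: where advance notice allows, participants are asked not to use asthma inhalers before the spirometry test; a rescue inhaler may be used whenever it is needed; usual inhaler use resumes as soon as the test is complete. Keep the seven-day record of timing and dosage as it is, since it identifies tests done after a dose. Carry the same wording into the Field Operations Guide and any participant instructions that mention inhalers.

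The cost is a short amendment, with no new procedure and no new data item. The one drawback is that a few more spirograms will be obtained after inhaler use. These can be identified from the existing record.
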